Pilot Study Evaluating the Hedonic Acceptability and Absorption of the Bioactive Compounds of a 5011-Nutrasorb Bar (Russian Tarragon Nutrasorb)

February 12, 2020

Background: Based on previous safety studies with 5011-Nutrasorb, it was decided to develop 30g into a high fat bar that would be acceptable in taste and that would provide detectable levels of 5011 in the circulation.

Objective: 5011-Nutrasorb can be formulated into a high fat (40% kcal from fat) bar that is safe and acceptable for human consumption and is compatible with detectable serum levels of the identified bioactive compounds within 6 hours of consumption

Phase 1

Aim 1: Formulate a bar containing 30 g of 5011-Nutrasorb and 40% fat. The goal is to develop a bar containing the following:

30 g PMI 5011-Nutrasorb (120 kcal)

20 g fat (100 kcal)

Remainder kcal (30) from carbohydrate and flavorings

Total kcal of bar – 250 kcal

Aim 2: Determine by visual analog scales the acceptability of the bar.

Study Design: 10 healthy participants will be enrolled into the study. The study will have a single testing visit. Once all 10 people have completed the study, the visual analog scales will be reviewed. The study may be repeated with the same 10 participants two additional times in case the first or second product is not acceptable. If the initial bar is not acceptable, the fat source and/or flavoring may be modified to improve acceptability.

Inclusion:

1. Healthy males or females between 18 and 50 years of age inclusive.
2. BMI 20-30 kg/m².

Exclusion:

1. Pregnant or currently lactating.
2. Taking any prescription medications.
3. Taking any OTC medications that cannot be stopped for test days.
4. Allergic to any ingredients contained in the bar.
5. Other conditions or situations that would interfere with the study or the participant's safety as determined by the investigators.

Testing Visit: The participants will come to the Pennington Biomedical Outpatient Clinic having had nothing but water from 10pm the prior night for the taste test. After appropriate written consent, participants will have their height and weight measured, BMI calculated and vital signs measured. Participants will also be asked about any medications that they may be taking. Following completion of these procedures, each participant will be

provided with a food bar and asked to consume the bar. After consumption, the participant will complete visual analog scales to rate the following: visual appeal, smell, taste, texture, aftertaste, and overall pleasantness.

Data Analysis: The visual analog scales will be reviewed and minimum thresholds will be set for each parameter. 6 out of 10 participants must rate the bar as acceptable to be considered a successful bar.

Phase 1 - Schedule of events

Test/Visit	Test Day
Taste Test	x
Visual Analog Scale	x
Adverse Events	x

Phase 2

Once an acceptable bar has been developed, phase 2 will begin.

Aim 3: Measure safety parameters (blood chemistry) pre and post bar consumption.

Aim 4: Measure bioactive compounds in the blood to determine absorption and PK parameters.

Study Design: 10 healthy participants will be enrolled into the study. The study will have a screening visit and a testing visit.

Inclusion:

1. Healthy males or females between 18 and 50 years of age inclusive.
2. BMI criteria 20-30 kg/m².

Exclusion:

1. Pregnant or currently lactating.
2. Taking any prescription medications.
3. Taking an OTC medications that cannot be stopped on testing day
4. Allergic to any ingredients contained in the bar.
5. A participant in phase 1 of the study.

56 Other conditions or situations that would interfere with the study or the participant's safety as determined by the investigators.

Screening visit: Participants will come to the screening visit having had nothing but water from 10pm the prior night. They will sign an informed consent after having all questions answered, complete a medical history questionnaire, have blood pressure, pulse, weight and height measured, and have blood drawn from an arm vein for a chemistry panel (less 2 teaspoons of blood). The chemistry panel will provide basic health information and participants may be excluded for abnormal lab values as determined by the study physician.

Testing Visit: The testing day will occur within 30 days of the screening visit. The participants will come back to the Pennington Biomedical Outpatient Clinic having had nothing but water from 10pm the prior night for the

testing visit. Each participant will be provided with a food bar and asked to consume the bar within 10 minutes. Blood samples will be taken prior to consumption of the bar (-10 minutes), baseline (time 0 after the bar is consumed) and at times 30, 60, 120 and 180 minutes post ingestion of the bar for glucose, insulin and bioactives.

Statistics: Normally distributed data will be analyzed by t-test and non-parametric data will be analyzed by chi squared testing or another appropriate statistical test.

Phase 2 - Schedule of events

Test/Visit	Screening	Test Day
Consent	x	
Chemistry Panel	x	x
Medical Questionnaire	x	
BP, Pulse & weight	x	
Height	x	
Bioactives		x
Taste Test		x
Visual Analog Scale		x
Adverse Events		x

Acceptability Visual Analog Questionnaire

Palatability Ratings

Smell

Taste

Texture

Aftertaste

Pleasant/Unpleasant (Please check)

Overall Pleasantness

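### The bar's fat line does not add up: 20 g of fat is about 180 kcal, not 100 kcal, so 20 g, 40% of energy and 250 kcal cannot all hold

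*Combined protocol and SAP*

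**What the plan says.** The composition of the bar is given once, under Phase 1, Aim 1, as a development target with four lines:

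- "30 g PMI 5011-Nutrasorb (120 kcal" for the active ingredient;
- "20 g fat (100 kcal" for the fat;
- "Remainder kcal (30) from carbohydrate and flavorings";
- "Total kcal of bar – 250 kcal".

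The Objective describes the product as a "high fat (40% kcal from fat) bar", which fixes the basis of the percentage as energy. Aim 1 opens by repeating the percentage without a basis: "Formulate a bar containing 30 g of 5011-Nutrasorb and 40% fat".

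The Phase 1 study design allows the source of fat, the flavoring or both to be changed if tasters reject the bar. It gives no alternative quantity of fat. Nothing in the document states an energy density for fat, describes a reduced-calorie fat, or says that the 20 g refers to an ingredient that is only partly fat.

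**The concern.** The fat line pairs a mass with an energy that do not correspond for ordinary fat. The 40% and the 250 kcal both depend on fat supplying 100 kcal, so the 20 g figure conflicts with both.

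The bar is the whole intervention, and its fat share is the feature the Objective uses to define it. Someone working from the gram figure would make a different product from someone working from the energy and percentage figures. Fat and energy content can plausibly affect the taste and texture ratings in both phases and the glucose, insulin and bioactive concentrations after ingestion in Phase 2. If the bar were made with 20 g of fat, those results would be reported for a product that does not match the Objective, and a reader could not tell from the protocol which bar had been eaten.

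**Working it through.** **Inputs from Aim 1 and the Objective.** Nutrasorb 30 g, 120 kcal; fat 20 g, 100 kcal; remainder 30 kcal; total 250 kcal; fat share 40% of energy.

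**Input not in the documents.** The energy density of fat, *e*. I assume 9 kcal/g and show 8 to 9.3 kcal/g.

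**Step 1: reproduce the plan's energy figures.**
- Total: 120 + 100 + 30 = 250 kcal, as stated.
- Fat share: 100/250 = 40%, as stated.
- Nutrasorb: 120/30 = 4 kcal/g, which is plausible.

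The energy column is coherent.

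**Step 2: test the gram figure.** Implied density of fat: 100/20 = 5 kcal/g. This is outside the assumed range, so the stated 100 kcal does not reproduce from 20 g.

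**Step 3: keep 20 g and leave the other two lines alone.** Fat energy = 20*e*; total = 150 + 20*e*; share = 20*e*/(150 + 20*e*). The last column gives the fat mass that would supply 100 kcal, 100/*e*.

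| *e* (kcal/g) | Fat energy (kcal) | Total (kcal) | Fat share | Grams for 100 kcal |
|---|---|---|---|---|
| 5 (implied by the plan) | 100 | 250 | 40% | 20 |
| 8 | 160 | 310 | 51.6% | 12.5 |
| 8.4 | 168 | 318 | 52.8% | 11.9 |
| 9 | 180 | 330 | 54.5% | 11.1 |
| 9.3 | 186 | 336 | 55.4% | 10.8 |

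At 9 kcal/g the fat supplies 80% more energy than stated (180/100), and the bar 32% more (330/250).

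**Step 4: check against the total.** Nutrasorb plus fat is 120 + 180 = 300 kcal at 9 kcal/g, and 120 + 160 = 280 kcal at 8 kcal/g. Both exceed 250 kcal before the 30 kcal remainder is added. The two lines alone exceed 250 kcal whenever *e* is above (250 − 120)/20 = 6.5 kcal/g.

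**Step 5: what each choice implies at 9 kcal/g.**
- Keep 100 kcal, 40% and 250 kcal: fat is 100/9 = 11.1 g, which is (20 − 11.1)/20 = 44% less than 20 g.
- Keep 20 g and the other two lines: 330 kcal, 54.5% of energy from fat.
- Keep 20 g and 40% of energy: total is 180/0.40 = 450 kcal, so the remainder is 450 − 120 − 180 = 150 kcal rather than 30.
- Keep 20 g and 250 kcal: fat is 180/250 = 72% of energy.

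**Step 6: could 40% be by weight?** 20/(30 + 20) = 40%, which may be where the 20 g came from. Adding about 7.5 g for the remainder (30 kcal at an assumed 4 kcal/g) gives 20/57.5 = 35%. Either way the Objective states the basis as energy, and a weight basis does not make 20 g equal 100 kcal.

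**The case against.** The strongest reply is that only one number is out of line. Fat energy, total energy, percentage and the Objective all agree, so the natural reading is a slip in the gram figure, and a formulator who followed the other figures would make the intended bar. In addition, Aim 1 sets a target for development rather than a locked recipe, Phase 1 may be run up to three times with modifications, and no sample size, acceptability threshold or statistical test uses these figures. The conflict also rests on an energy factor from outside the documents, and it would vanish if the 20 g were a fat-containing ingredient at 5 kcal/g. Even at 20 g, the bar would still be high in fat.

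Some of this stands. The document's own balance does favor the energy figures, and the error has no effect on the operating characteristics of the trial. The harm is conditional on a bar being made to the gram figure, and the documents do not show which bar was made.

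The rest does not remove the problem. The answer is the same across 8 to 9.3 kcal/g. No text describes a 5 kcal/g fat, and if one was meant the protocol needs to say so. If some of the 20 g were already within the Nutrasorb, 20 g in a 250 kcal bar would still be 72% of energy at 9 kcal/g. The permitted changes cover the source of fat and the flavoring, not its amount. A target whose parts conflict cannot guide formulation or show whether Aim 1 has been met.

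**Conclusion.** The concern holds. At any ordinary energy density of fat, 20 g of fat, 40% of energy from fat and 250 kcal cannot all be true. The intended fat dose lies between about 11 g and 20 g, nearly a twofold difference. At 9 kcal/g, a bar made to the gram figure with the other lines unchanged would be 330 kcal and 54.5% fat by energy; over 8 to 9.3 kcal/g the ranges are 310 to 336 kcal and 51.6% to 55.4%.

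The conclusion rests on the assumed energy factor and on reading the 20 g as plain fat, which is how the line is written. Because this is a wrong figure in the only specification of the sole intervention, it should be corrected before manufacture.

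**What to change.** Before any bar is made, reconcile four quantities so that they agree: grams of fat, energy from fat, percentage of energy from fat, and total energy. Two self-consistent versions at 9 kcal/g are:

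- about 11 g of fat, 100 kcal, 40% of energy, 250 kcal total; or
- 20 g of fat, 180 kcal, 54.5% of energy, 330 kcal total, with the 40% in the Objective changed to match.

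The sponsor must decide which is intended. The first leaves the Objective and every energy figure as they stand. If the 20 g refers to a reduced-calorie fat or to an ingredient that is only partly fat, name it and give its energy density. State the basis of the 40% in Aim 1 as well as in the Objective, and report the composition of each bar as made alongside its results.

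The cost is protocol wording only, with no added participants or procedures.

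### Aim 2 is answered from whichever Phase 1 round first reaches 6 of 10, so the acceptability rate is biased upward; the Phase 2 ratings already scheduled in 10 new people could give an unselected estimate.

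*Combined protocol and SAP*

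**What the plan says.** - **Rounds.** Phase 1, Study Design, enrols 10 people for one tasting and then allows more: "The study may be repeated with the same 10 participants two additional times in case the first or second product is not acceptable". That is up to three rounds.
- **Reformulation.** The same paragraph continues: "If the initial bar is not acceptable, the fat source and/or flavoring may be modified to improve acceptability". Changing the recipe is foreseen but optional.
- **Pass rule.** Phase 1, Data Analysis: "6 out of 10 participants must rate the bar as acceptable to be considered a successful bar". The cut-offs behind an acceptable rating have no values yet: "The visual analog scales will be reviewed and minimum thresholds will be set for each parameter".
- **Consequence of a pass.** Phase 2 opens with: "Once an acceptable bar has been developed, phase 2 will begin". The first passing bar therefore ends Phase 1.
- **Phase 2 raters.** The exclusion list includes "A participant in phase 1 of the study", so all 10 Phase 2 participants are new. The Phase 2 schedule of events ticks a taste test and the "Visual Analog Scale" on the test day. The Phase 2 testing-visit text has no rating step, Aims 3 and 4 cover only safety chemistry and absorption, and the Statistics paragraph names no acceptability analysis.

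**The concern.** Acceptability is Aim 2 and part of the stated Objective, so the Phase 1 result is more than an internal development gate. Testing stops at the first round with at least 6 acceptances, and that round supplies the answer. A proportion reported only because it reached 60% tends to exceed the true proportion, and allowing up to three attempts raises the chance that some round gets there. The reported acceptability of a mediocre bar could then look clearly favourable. The plan has a remedy within reach, because 10 people who played no part in choosing the bar are scheduled to rate it, but it gives those ratings no stated purpose.

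**Working it through.** The plan gives no target rate, unacceptable rate, error level or sample-size reasoning, so it has no figure of its own to reproduce. What follows evaluates its rule.

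**Inputs from the plan:** n = 10 tasters; pass if at least 6 accept; at most 3 rounds; same tasters; stop at the first pass.

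**Assumptions:** each person's ratings reduce to accept or not accept; the true acceptability p is varied; p is at first held equal across rounds. Correlation between one taster's ratings across rounds is modelled by a latent normal person effect with rho from 0 to 0.8 (simulation, at least 200,000 runs per setting).

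**1. Chance of passing one round.** P = sum over x = 6 to 10 of C(10,x) p^x (1−p)^(10−x).
- p = 0.4: 0.1115 + 0.0425 + 0.0106 + 0.0016 + 0.0001 = 0.166 after rounding
- p = 0.5: 0.2051 + 0.1172 + 0.0439 + 0.0098 + 0.0010 = 0.377

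**2. Chance of passing within three rounds.** With independent ratings this is 1 − (1 − P)^3. The correlated figures are simulated.

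| True p | One round | Three, independent | Three, rho 0.3 | Three, rho 0.8 | Ratio to one round |
|---|---|---|---|---|---|
| 0.4 | 0.166 | 0.420 | 0.39 | 0.31 | 1.9 to 2.5 |
| 0.5 | 0.377 | 0.758 | 0.70 | 0.59 | 1.6 to 2.0 |

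**3. Observed rate given a pass.** E = [sum over x = 6 to 10 of (x/10) × Pr(x)] / P. At p = 0.4 this is 0.1066 / 0.1662 = 0.641; at p = 0.5 it is 0.2500 / 0.3770 = 0.663.

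| True p | One round | Three, independent | Three, rho 0.8 | Overstatement (points) |
|---|---|---|---|---|
| 0.4 | 0.641 | 0.641 | 0.633 | 23–24 |
| 0.5 | 0.663 | 0.663 | 0.652 | 15–16 |
| 0.8 | 0.811 | 0.811 | 0.808 | about 1 |

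The one-round and three-round columns agree under independence, and correlation lowers the figure slightly. Conditioning on a pass therefore produces the overstatement; the number of rounds does not.

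**4. If reformulation works.** Suppose true rates of 40%, 60% and 70% in rounds 1 to 3 (an assumption). The average gap between the observed rate in the passing round and that bar's own true rate is then about 11 points at rho = 0, falling to about 8 at rho = 0.8.

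**5. An unselected sample of 10.** The bar is fixed before the Phase 2 participants taste it, so the expected observed rate equals its true rate in such people under Phase 2 conditions. Precision remains poor: 6 of 10 has an exact 95% interval of 26% to 88%.

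**The case against.** The strongest reply is that this is product development in a pilot. Aim 1 is to formulate a bar, the repeats are meant for changed products, and re-using tasters lets formulations be compared within person. Holding acceptability equal across rounds is then close to a worst case. This stands: the repeats are legitimate, and successful reformulation reduces the overstatement. Because modification is optional, equal acceptability is still possible under the text.

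A reader might infer four stronger things that the documents do not support:
- **That three attempts more than double the chance of a pass.** That holds at 40% and 50% only with independent or weakly correlated ratings. With the same tasters returning, correlation is likely, and the ratio falls as low as 1.9 at 40% and 1.6 at 50%.
- **That the repeats cause the 24-point overstatement.** A single round gives the same figure.
- **That later bars are rated against the memory of a rejected one.** Nothing in the plan shows such an effect or its direction, and no figure here depends on it.
- **That only the passing round will be reported, or that the Phase 2 ratings will be discarded.** The plan says neither. The Statistics paragraph is generic and does not exclude the scales; what is missing is a stated use for them.

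It can also be said that the remedy leaves the chance of a poor bar entering Phase 2 unchanged. That is true. The remedy concerns the acceptability estimate, not the gate.

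**Conclusion.** The point holds as a moderate, inexpensive improvement. As written, Aim 2 rests on a round selected for passing. If acceptability does not change between rounds, allowing up to three raises the chance of a pass about 1.6- to 2.5-fold for bars that 40% to 50% of people would accept. Given a pass, the observed rate is too high by 23–24 points at true 40%, 15–16 at true 50% and about 1 at true 80%. The selected round alone cannot show which of these cases applies.

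The sizes depend on assumed true rates and on the assumed correlation within tasters. They leave out any extra flexibility from setting the cut-offs after the scales have been reviewed. The finding does not call the 6-of-10 rule or the repeats unsuitable as a development gate.

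**What to change.** 1. Keep the repeats and 6 of 10 as the go rule for starting Phase 2.
2. Fix the visual analog cut-offs, and how they combine into one acceptable or not acceptable result per person, before any Phase 2 ratings are seen.
3. State in Statistics that the Aim 2 acceptability estimate is the count of acceptances among the 10 Phase 2 participants, with an exact 95% interval.
4. Add the rating step to the Phase 2 testing-visit text so that it agrees with the schedule of events.
5. Report the result of every Phase 1 round, noting any recipe change.

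**Cost:** a few sentences in Data Analysis, Statistics and the Phase 2 visit text, with no new participants or measurements. The estimate arrives later, may be less favourable, and stays imprecise with 10 people. Phase 2 tasting conditions also differ somewhat (a 10-minute limit for eating the bar, and serial blood draws), which the report should mention.

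### In Phase 1, visual appeal and smell are rated only after the bar has been eaten, so both ratings come from memory and are open to influence from taste and aftertaste (minor).

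*Combined protocol and SAP*

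**What the plan says.** In Phase 1, under Testing Visit, each participant is "provided with a food bar and asked to consume the bar". The ratings come next, on a single occasion: "After consumption, the participant will complete visual analog scales to rate the following: visual appeal, smell, taste, texture", with aftertaste and overall pleasantness completing the list.

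Under Data Analysis, the use of the scales is described in two sentences: "The visual analog scales will be reviewed and minimum thresholds will be set for each parameter", and "6 out of 10 participants must rate the bar as acceptable to be considered a successful bar".

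Under Study Design for Phase 1, the size and format are "10 healthy participants will be enrolled into the study. The study will have a single testing visit". Up to two repeat rounds with the same people are allowed if the product fails, and the stated response to failure is: "If the initial bar is not acceptable, the fat source and/or flavoring may be modified to improve acceptability".

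**The concern.** Appearance and smell can be judged when a food is presented. Taste, texture, aftertaste and overall pleasantness can be judged only by eating it. The plan collects both groups after eating. By then the bar itself is no longer there to look at or smell, and the participant has formed an opinion of the whole product. A disliked aftertaste could pull the smell or appearance score down, and a liked taste could lift it.

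Acceptability on these scales is Aim 2, and Phase 2 does not begin until there is an acceptable bar. If the first bar fails, the sponsor will look at the attribute scores for guidance on what to change. Scores that partly reflect the overall eating experience are poorer guidance than scores that reflect one attribute each.

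**Working it through.** The plan gives no figure to reproduce on this point. The check is of the order of procedures, followed by a count of what is affected.

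**1. Order of procedures (Phase 1, Testing Visit).** Measurements and medication questions, then the bar is provided, then it is eaten, then all six scales are completed. There is one rating occasion.

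**2. Is there an earlier rating anywhere else?**
- The Phase 1 schedule of events has one row for the visual analog scale on the test day, with no time relative to eating.
- The questionnaire at the end of the document is a single list of attributes, with no division into before and after eating.
- No partial portion, second bar or retained sample is mentioned.

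Nothing qualifies the Testing Visit text.

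**3. What can be observed at the time of rating, if the bar is finished as asked?**
- Visual appeal: the bar has been eaten; rated from memory.
- Smell: the bar has been eaten; rated from memory.
- Taste, texture, aftertaste, overall pleasantness: just experienced; after eating is the right time.

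**4. Are the two affected scales used separately?** Yes, by intent. The plan says that "minimum thresholds will be set for each parameter", and visual appeal and smell are among the parameters. The values are not given, and neither is the rule that turns six cut-offs into one verdict per participant.

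**5. Extent.**
- Scales affected: 2 of 6, or 2/6 = 33%.
- Ratings affected per round: 2 × 10 = 20 of 6 × 10 = 60.
- If all three permitted rounds take place: 3 × 20 = 60 of 180. Rounds 2 and 3 are conditional on failure.

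These are counts of exposed ratings. They do not measure bias.

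**6. Sensitivity of the success rule, for context only.** Let p be the true probability that a participant rates the bar acceptable; its value is an assumption. With 10 participants treated as independent, the chance of success is P(X ≥ 6) = Σ C(10,k) p^k (1−p)^(10−k), for k = 6 to 10.
- p = 0.4: 0.166
- p = 0.5: (210 + 120 + 45 + 10 + 1)/1024 = 386/1024 = 0.377
- p = 0.6: 0.633
- p = 0.7: 0.850
- p = 0.8: 0.967

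A change in p from 0.5 to 0.6 would move the chance of success by 0.633 − 0.377 = 0.256, about 26 percentage points. This shows that a 10-person rule reacts strongly to shifts in overall acceptance. It does not show that the timing of two scales produces such a shift.

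**The case against.** The strongest reply is that nothing of consequence has been shown to follow.

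- **The influence is inferred.** The documents contain no evidence that taste alters these scores. Participants see and smell the bar as they eat it, and no delay before rating is stated, so the recall interval may be short. This stands as a limit on the claim: the ratings are recalled, and they are open to influence, but whether they shift, how far and in which direction is unknown.
- **The available changes are few.** Only fat source and flavoring are named as things to modify. A cleaner visual appeal score has no named action attached, and smell, taste and aftertaste may all point to flavoring. This stands in large part. The gain for reformulation is limited and lies mainly with smell.
- **The link to the decision is undefined.** The verdict per participant might require all six cut-offs, overall pleasantness alone, or something else. This stands. A reader might infer that the present order could wrongly pass or fail a bar, or might read the 26-point figure as the size of the problem. The documents support neither, because they do not connect these two scales to the success rule.
- **Repeat rounds use the same people.** They will bring expectations from earlier bars, so rating before the first bite is not free of taste expectation in rounds 2 and 3. This stands. The change still means that each new bar is seen and smelled before it is tasted.
- **The form may not carry a visual appeal item.** The questionnaire as it can be read lists smell but not visual appeal. That may be lost text, so it should be checked against the original form and is not counted here as an error. If the item is truly absent, the point holds for smell alone.

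None of this defends rating appearance and smell after the bar has been eaten. It bears on how much weight the point carries.

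**Conclusion.** The point holds as a minor measurement weakness. In Phase 1, two of the six scales are completed from memory after the participant knows the taste and aftertaste, which makes visual appeal and smell less reliable as separate measurements. The extent is 20 of 60 ratings per round; the size and direction of any shift cannot be derived from the documents.

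The conclusion assumes that the bar is finished before the form is completed, as the text implies, and that both attributes appear on the form in use.

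A reader might also infer that the same change is needed in Phase 2. The documents do not support that. The Phase 2 schedule lists the scale on the test day without a time relative to eating, and the Phase 2 aims concern safety chemistry and absorption, with no acceptability decision.

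**What to change.** In the Phase 1 Testing Visit, state that in each round the participant completes the visual appeal and smell scales when the bar is presented, before the first bite, and completes taste, texture, aftertaste and overall pleasantness after eating. Split the questionnaire into a before-eating part and an after-eating part to match, and confirm while doing so that visual appeal is on it.

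The cost is one sentence, a divided form and about one minute per participant, with no added staff or procedure. The change does not remove expectations carried over from earlier bars in rounds 2 and 3; that limit should be acknowledged when scores are compared across rounds.

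### The 6-of-10 acceptability gate has no VAS cut-off or combining rule fixed before tasting, and the thresholds appear to be set after the scores are in

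*Combined protocol and SAP*

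**What the plan says.** Aim 2 in Phase 1 is to "Determine by visual analog scales the acceptability of the bar". Under Testing Visit, six ratings are collected: "After consumption, the participant will complete visual analog scales to rate the following: visual appeal, smell, taste, texture, aftertaste, and overall pleasantness".

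The timing of the review is in the Phase 1 Study Design: "Once all 10 people have completed the study, the visual analog scales will be reviewed". The Phase 1 Data Analysis paragraph then states: "The visual analog scales will be reviewed and minimum thresholds will be set for each parameter". It goes straight on to the gate: "6 out of 10 participants must rate the bar as acceptable to be considered a successful bar".

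Two consequences hang on that gate:

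- Failure can lead to another round: "The study may be repeated with the same 10 participants two additional times in case the first or second product is not acceptable".
- Success opens the next phase: "Once an acceptable bar has been developed, phase 2 will begin".

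**The concern.** The count of 6 out of 10 is fixed, but what is being counted is not. Two things are plainly absent from the document: a numerical cut-off on any scale, and a rule that converts one person's six ratings into a single verdict.

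A third point is inferred. The review takes place after all ten people finish, and threshold-setting is joined to that review in one sentence, in the future tense. No earlier step or value is described, so the natural reading is that thresholds are chosen once the scores are known.

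If participant verdicts are then derived from those thresholds, the outcome of the gate depends on a choice made after seeing the data. Even without any such steering, two teams following the protocol faithfully could reach opposite verdicts from the same ten forms. Acceptability is part of the trial's stated objective. The gate is the only stated criterion for Aim 2 and for moving to Phase 2, and it also decides whether the same ten people are asked back for a reformulated bar.

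**Working it through.** **Inputs.** From the plan: 10 tasters, success at 6 or more, six scales, up to three rounds (the first plus two repeats). The plan gives no target acceptance rate, error rate or VAS data, so there is no stated figure to reproduce. Every score distribution below is an assumption made for illustration.

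**Step 1: the gate once a verdict is defined.** If each taster finds the bar acceptable with probability p, then P(pass) = Σ C(10,k) p^k (1−p)^(10−k), summed over k = 6 to 10.

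| p | 0.3 | 0.4 | 0.5 | 0.6 | 0.7 | 0.8 |
|---|---|---|---|---|---|---|
| P(pass) | 4.7% | 16.6% | 37.7% | 63.3% | 85.0% | 96.7% |

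The curve is steep between 0.4 and 0.7, so any choice that shifts p in that range largely decides the result.

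**Step 2: a cut-off chosen after the scores are seen.** On one scale, at least six people meet a cut-off exactly when it is at or below the sixth-highest score. If all six scales must be met, cut-offs at or below the lowest score on each scale are sufficient. A passing cut-off of this kind therefore exists unless the scale's own floor prevents it.

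It need not look lax. Assume normal scores truncated to 0–100, with mean 45 and SD 20 before truncation. The sixth-highest of ten then has median 43 (5th–95th centile 30–55), and the lowest has median 17 (3–33).

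**Step 3: sensitivity to the cut-off.** Same assumed distribution; p is the probability that a score reaches the cut-off.

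| Cut-off | p (mean 45, SD 20) | P(pass) | P(pass) over mean 40–55, SD 15–25 |
|---|---|---|---|
| 50 | 0.404 | 17% | 2–71% |
| 40 | 0.605 | 65% | 38–99% |
| 30 | 0.782 | 95% | 83–100% |

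For a given bar in that range, moving the cut-off from 50 to 30 adds 29 to 90 percentage points. At mean 60 it adds 8 to 27 points, so the problem concerns borderline bars.

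**Step 4: sensitivity to the combining rule, with cut-offs fixed.** Assume a proportion q of people meet each scale's cut-off, with a common inter-scale correlation of 0.4 to 0.8 on an underlying normal scale. Find the probability that one person satisfies the rule, then apply the formula in Step 1.

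| q per scale | Overall pleasantness alone | At least four of six | All six |
|---|---|---|---|
| 60% | 63% | 51–56% | 0.4–12% |
| 70% | 85% | 82–83% | 4% to about a third |
| 80% | 97% | 96–98% | 23–67% |

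The missing rule can make the gate lax or strict, so no single direction of error is implied.

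**Step 5: repeat rounds and precision.** With p = 0.5, one round passes 37.7% of the time. Three independent rounds would pass at least once with probability 1 − (1 − 0.377)³ = 75.8%. This is only indicative, because the same people taste again and the recipe may change, but it shows that the passing round is a selected one. An observed 6/10 has an exact 95% CI of 26–88%.

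**The case against.** The data-dependence argument needs two inferences: that thresholds are set after the scores are seen, and that verdicts come from the thresholds. The plan states neither outright. Reviewing the scales and setting thresholds could be separate steps. The gate speaks of participants rating the bar as acceptable, which taken literally is the participant's own judgement. The questionnaire carries a pleasant-or-unpleasant check that might supply it. On that reading a cut-off could not force a pass.

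This stands as a limit on the conclusion. Aim 2 favours the threshold reading, but the text does not settle it. The form as extracted does not show whether the check is a separate item or the response format for overall pleasantness, so nothing here relies on it. If a direct answer is intended, the plan never names the item, and the thresholds then have no stated purpose. Clarification is needed on either reading.

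It is also fair that the magnitudes are all assumed, and that Steps 3 and 4 show sensitivity to an undefined rule rather than bias from a later choice; only Step 2 bears on the latter. Finally, this is a ten-person formulation step with no hypothesis test, and Phase 2 already plans ratings from new people. That limits the damage, but the gate still has no determinate meaning as written.

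**Conclusion.** The concern holds and should be fixed. It is certain that no cut-off and no combining rule are given. It is inferred, from two adjoining statements and the absence of any earlier step, that thresholds are set after tasting. It is conditional on threshold-derived verdicts that the scores can then shape the gate.

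Under the illustrative assumptions, an unfixed cut-off moves the pass probability of a borderline bar by 29 to 90 points. An unfixed combining rule moves it from about 85% to between 4% and a third when 70% of people meet each scale. A clearly liked bar is much less exposed to the choice of cut-off.

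Only the acceptability conclusion and the decision to start Phase 2 are affected. The safety and absorption aims are not biased by this, and no stated error rate is breached.

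**What to change.** Before the first bar is served, the protocol should state:

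1. **The verdict rule.** Give the numerical cut-off(s) and one rule for when a participant finds the bar acceptable. One option is overall pleasantness at or above a stated VAS value, with the other five scales descriptive and used to guide reformulation. Six stated cut-offs with the number that must be met would also do. If a direct participant answer is intended, say so and name the item.
2. **Constancy.** The same cut-off(s) and rule apply in every round.
3. **Use of 6/10.** Keep it as a go/no-go rule only, and report which round passed.
4. **The reported estimate.** Because the passing round is selected, report acceptability with an exact 95% CI from the VAS in the Phase 2 schedule of events, using the same definition. Those raters are new, since the Phase 2 exclusions list "A participant in phase 1 of the study". The Phase 2 Testing Visit text does not describe this VAS and should be brought into line with the schedule.

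The first two items cure the defect itself; the last two deal with selection over rounds.

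The cost is three or four sentences, with no new visits and no data beyond the VAS already scheduled. The downsides are that the cut-off cannot be tuned later, the reported acceptability may be less favourable, and ten people still give a wide interval (6/10: 26–88%; 8/10: 44–97%).
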